#### **b. Secondary Efficacy Endpoint:**

The secondary efficacy endpoints will focus on more detailed analysis of glycemic control, and will include the following:

- 1) **Insulin independence:** We will evaluate the proportion of patients presenting with insulin independence while fulfilling the primary endpoint at 1 year after the first and 1 year after the last islet cell infusion, respectively.

#### **Definition of insulin-independence:**

[figure not shown]
- Absence of exogenous insulin injection

- Fasting capillary glucose level should not exceed 140 mg/dL (7.8 mmol/L) more than three times in the past week based on measuring capillary glucose levels a minimum of 7 times in a seven day period.
  - Fasting plasma glucose level  $\leq$  126 mg/dL (7.0 mmol/L); if the fasting plasma glucose level is  $>$  126 mg/dL (7.0 mmol/L), it must be confirmed in an additional one out of two measurements.
  - 2-hour postprandial capillary glucose should not exceed 180 mg/dl (10.0 mmol/L) more than one out of every seven times in the past week based on measuring capillary glucose levels a minimum of 7 times in a seven day period (for the modification see Section 2.9 Changes from the Planned Protocol Analysis).
  - Evidence of endogenous insulin production defined as fasting or stimulated C-peptide levels  $\geq$  0.5 ng/mL (0.16 nmol/L)
- 2) **Hypoglycemic episodes** will be measured by the number and severity of hypoglycemic episodes quantified by the Ryan HYPO Score, and the percent reduction will be reported.
- 3) **Glucose variability and hypoglycemia duration will be measured by continuous glucose monitoring system (CGMS)** for a 3-day period at three different time points: 1) at screening, 2) one year after first islet transplant, and 3) one year after last islet transplant. The following measurements and analysis will be reported:
- Mean glucose concentration
  - Percent of time in the following ranges:
    - < 60 mg/dl
    - 60-140 mg/dl
    - 141-200 mg/dl
    - > 200 mg/dl

## 2.8. Sample Size and Power Considerations

For the primary endpoint (composite HbA1c  $\leq$  6.5% and absence of severe hypoglycemic events), we expect 80% of the transplant population to achieve this endpoint. Therefore, assuming a sample size of 50, a two-sided 95.0% confidence interval for a single proportion will extend  $\pm$  0.111 from the observed proportion. When the sample size is 40, a two-sided 95.0% confidence interval for a single proportion will extend  $\pm$  0.124 from the observed proportion (Figure 1). Proportion and surrounding confidence interval will be reported.

**Figure 1.** Sample Size Curve for 95% Confidence Interval for Proportion

From recent CITR report, the population rate of favorable outcome under standard insulin treatment for T1D patients indicated as eligible for islet transplant is below 1% (Tiwari et al., 2012). Historical data on islet transplants performed at multiple sites in North America show that the observed favorable outcome rate is at least 70% across all centers. An increase of 50% in the rate of favorable outcome is considered the minimal difference needed to show clinically meaningful benefit. The power of a single-arm trial at a one-sided significance level 0.05 with varying sample sizes and varying observed favorable outcome rates is shown in Table 1.

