#### **9.1.1. Analysis of Primary Endpoints**

The primary analysis is to estimate the true rate of this composite favorable outcome at one year in patients in the ITT population. The proportion of favorable outcomes will be used as the point estimate. An exact (Clopper-Pearson) two-sided 95% confidence interval will be constructed assuming an underlying binomial distribution for the ITT population via SAS:

```
proc freq data=dataset order=freq;  
  
    tables binary_outcome / binomial(exact) alpha=.05;  
  
run;
```

Failure to achieve the favorable outcome will be summarized in two sub-groups: the rate of patients having an HbA1c  $>$  6.5% at Day 365, and the rate of patients who experienced any SHE from Day 28 to Day 365.

The primary endpoint will be assessed for all treated patients from first transplant (including patients with  $>$ 1 transplant within 1 year of first exposure) and from last transplant. A patient's HbA1c results may be reported on visit days that do not fall on the exact Day 365. In this case the records from the date that is the closest to and within 4 weeks (28 days) before or after Day 365 will be used.

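### The stated precision (±0.111 at n=50, ±0.124 at n=40) is that of a Wald interval, but the specified analysis is Clopper-Pearson, whose lower arm is about a quarter longer

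*SAP*

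**What the plan says.** SAP 2.8 plans the trial around precision for the composite primary endpoint. It states "we expect 80% of the transplant population to achieve this endpoint" and gives two scenarios. The first, "assuming a sample size of 50", says that "a two-sided 95.0% confidence interval for a single proportion will extend" ±0.111 from the observed proportion. The second, "When the sample size is 40", gives ±0.124. The interval method is not named. Protocol 6.10.2 carries the same two figures, also without a method.

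SAP 9.1.1 does name one: "An exact (Clopper-Pearson) two-sided 95% confidence interval will be constructed assuming an underlying binomial distribution for the ITT population". The SAS code printed there requests the exact binomial option at alpha 0.05. SAP 2.9, which lists changes from the protocol analysis, mentions neither an interval method nor a revised precision.

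SAP 2.8 also says that at least 50 patients had been planned, and goes on to defend as few as 15 on grounds of power. It gives no interval width for any size below 40.

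**The concern.** An exact binomial interval around 80% cannot extend the same distance on both sides, so the planning statement and the analysis specification cannot describe the same interval. If the ± figures come from a normal approximation, they understate the distance from the estimate down to the lower limit.

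That side matters most here. The trial has a single arm and is meant to support a licence application. SAP 2.8 takes the rate under standard insulin treatment as below 1% and sets an increase of 50% as the smallest clinically meaningful benefit. How far the lower limit sits above roughly one half is what a reader will look at. Anyone who carries the stated formula down to the smaller sizes now in view would expect a noticeably higher lower limit than the specified analysis will give.

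**Working it through.** **Inputs.** Observed proportion 0.80 and n = 50 or 40 (SAP 2.8; protocol 6.10.2); two-sided 95%; interval method Clopper-Pearson (SAP 9.1.1). At 80% the success counts are 40/50 and 32/40.

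**Step 1: reproduce the stated figures.** The Wald half-width is 1.96 × √(0.8 × 0.2 / n).

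- n = 50: 1.96 × √0.0032 = 0.1109, which rounds to the stated 0.111.
- n = 40: 1.96 × √0.0040 = 0.1240, which rounds to the stated 0.124.

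Other methods do not fit the text. Wald with continuity correction gives 0.1209 and 0.1365. Wilson gives unequal arms (lower/upper) of 0.130/0.088 and 0.148/0.095. Jeffreys gives 0.126/0.092 and 0.142/0.101. The Agresti-Coull half-width also rounds to 0.111 and 0.124, but that interval is centred on (x+2)/(n+4), i.e. 42/54 = 0.778 and 34/44 = 0.773. The SAP measures its distances from the observed proportion, so Wald is the reading that fits.

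**Step 2: apply the specified method.** The Clopper-Pearson lower limit is the 0.025 quantile of Beta(x, n−x+1). The upper limit is the 0.975 quantile of Beta(x+1, n−x). The first two rows below are the SAP's own precision scenarios. The last three use the other sizes in SAP Table 1, for which no interval width is stated, and are illustrative.

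| Successes / n | Wald half-width | Exact 95% limits | Lower arm | Upper arm | Lower arm ÷ Wald |
|---|---|---|---|---|---|
| 40/50 | 0.1109 | 0.6628 to 0.8997 | 0.1372 | 0.0997 | 1.24 |
| 32/40 | 0.1240 | 0.6435 to 0.9095 | 0.1565 | 0.1095 | 1.26 |
| 24/30 | 0.1431 | 0.6143 to 0.9229 | 0.1857 | 0.1229 | 1.30 |
| 16/20 | 0.1753 | 0.5634 to 0.9427 | 0.2366 | 0.1427 | 1.35 |
| 12/15 | 0.2024 | 0.5191 to 0.9567 | 0.2809 | 0.1567 | 1.39 |

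**Step 3: size of the gap.**

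- Lower limit: the exact limit lies below the Wald limit by 0.1372 − 0.1109 = 0.0263 at n = 50, 0.1565 − 0.1240 = 0.0325 at n = 40, and 0.2809 − 0.2024 = 0.0785 at n = 15.
- Upper arm: 0.0997/0.1109 = 0.90 at n = 50 and 0.1095/0.1240 = 0.88 at n = 40, so it is shorter than stated.
- Average half-width: (0.8997 − 0.6628)/2 = 0.1184 and (0.9095 − 0.6435)/2 = 0.1330, each about 7% above the stated figure.

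**Step 4: does this depend on observing exactly 80%?** Averaged over the binomial distribution with a true rate of 0.8, the expected exact lower arm is 0.136 at n = 50 (22% above Wald) and 0.154 at n = 40 (24% above). The conclusion does not hinge on the single outcome.

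**Step 5: what the stated precision would need.** At 80%, the exact lower arm is 0.113 with 70 patients and 0.108 with 75. A lower arm of 0.111 would therefore take between 70 and 75 patients, not 50.

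**The case against.** The best counter-argument concerns weight. SAP 9.1.1 frames the primary analysis as estimation, no success threshold is tied to the interval, and neither document sets a required width. The interval that will be reported is already fixed by method and code, so correcting SAP 2.8 alters no result. The two figures are arithmetically right for the formula behind them and sit in a section that summarises the protocol. The longer lower arm is partly offset by a shorter upper one. At 50 and 40 patients the exact lower limits still clear a benchmark near 51% (a rate below 1% plus 50%) by a wide margin, and even 12/15 stays just above it. The protocol names no interval method, so it does not contradict itself.

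All of this stands and limits the consequence. It does not reconcile the two SAP sections. Section 2.8 tells the reader how far the interval will extend, and the interval specified in 9.1.1 will not extend that far on one side and will extend further on the other. The 15-patient row is not an error in a stated figure, since none is given for that size; it only shows where the stated formula would lead.

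**Conclusion.** The concern holds. The precision in SAP 2.8 and protocol 6.10.2 is not what the specified primary analysis delivers. At an observed 80% the exact lower arm is 0.137 against 0.111 (24% longer) with 50 patients, and 0.156 against 0.124 (26% longer) with 40.

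That the planning formula was Wald is inferred from the reproduction of both figures, since neither document names it. The mismatch does not rest on that inference, because no symmetric ± figure can describe the exact interval at 80%. This is a planning-to-analysis inconsistency that should be corrected. It does not threaten the validity of the trial or of the interval to be reported.

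**What to change.** In SAP 2.8, drop the ± wording, name Clopper-Pearson, and state the limits expected at 80%: 0.663 to 0.900 for 40/50 and 0.644 to 0.909 for 32/40. Redraw the sample-size curve (Figure 1) if it was built on the same formula. Since the section now argues for fewer patients, add the exact limits for the smaller sizes in Table 1: 0.614 to 0.923 (24/30), 0.563 to 0.943 (16/20) and 0.519 to 0.957 (12/15). A row for the number expected at the data cut-off would also help, but the documents do not give that number and the sponsor would have to supply it.

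Protocol 6.10.2 should carry the same figures at its next revision. Until then, an entry in SAP 2.9 recording the interval method and the restated precision would do.

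The cost is editorial: the figures become slightly less favourable on the lower side, and no design, endpoint or analysis changes.

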**Table 1. Power of a single-arm trial at a one-sided significance level 0.05**

	Sample Size			
	15	20	30	50
Observed Favorable Outcome Rate (%)	Power for the true improvement of the favorable outcome rate to be at least 50% (%)			
65	32	39	51	70
70	50	60	75	91.5
75	71	81	93	99.1
80	88	95	99.2	>99.9

We had planned to enroll at least 50 patients. However, with as few as 15 patients and an observed favorable outcome rate at 80%, we will have 88% of power to show the true treatment effect that at least 50% more of T1D patients than those under standard insulin treatment will attain the favorable outcome through the UIC islet transplantation treatment.

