### **2.3. Planned Number of Patients**

The study plans to perform islet transplants for 50 or more patients. Please see Section 2.8 for sample size and power considerations.

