### **2.7.2 Efficacy:**

#### **a. Primary Efficacy Endpoint:**

The proportion of patients with an HbA1c  $\leq 6.5\%$  and free of severe hypoglycemic events at 1 year after the first and 1 year after the last islet cell infusion, respectively (for the addition of time point see Section 2.9 Changes from the Planned Protocol Analysis).

Standard insulin treatment can rarely improve glycemic control in brittle Type 1 diabetic patients who are already on state-of-the-art insulin therapy. The rate of aforementioned favorable outcome achieved under standard insulin treatment over-a-year from a population-based diabetes registry database is as low as 0.3% (Tiwari et al., 2012). In general these patients require insulin reduction to reduce hypoglycemic episodes, which would likely lead to higher HbA1c. In contrast, islet transplantation can reduce hypoglycemic episodes without increasing HbA1c.

The protocol definition of severe hypoglycemic event: An event with symptoms compatible with hypoglycemia in which the patient required the assistance of another person and which was associated with either a blood glucose level  $< 50$  mg/dl (2.8 mmol/L) or prompt recovery after oral carbohydrate, intravenous glucose, or glucagon administration.

A broader clinical definition of severe hypoglycemic event that will apply to some of the exploratory endpoints as described later: receiving any of third-party assistance to treat a hypoglycemic reaction would sufficiently determine the occurrence of a SHE, regardless of blood glucose levels which may or may not be available.

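### SAP Table 1 claims 88% power with 15 patients at an 80% rate; by the exact binomial, the power to exclude the SAP's own 50-point threshold is 64.8%

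*SAP*

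**What the plan says.** SAP section 2.8 gives two justifications for the sample size. The first is interval width: about ±0.111 at 50 patients and an 80% rate. The second is a power argument for a single-arm comparison with a fixed threshold. It says that "An increase of 50% in the rate of favorable outcome is considered the minimal difference needed to show clinically meaningful benefit", and it puts the comparator rate low: "the population rate of favorable outcome under standard insulin treatment for T1D patients indicated as eligible for islet transplant is below 1" per cent. Section 2.7.2 gives a figure for the same comparator, which "from a population-based diabetes registry database is as low as 0.3" per cent. "The power of a single-arm trial at a one-sided significance level 0.05" is then tabulated in Table 1 for 15, 20, 30 and 50 patients and for favourable outcome rates of 65%, 70%, 75% and 80%. The rates are labelled as observed.

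The paragraph after the table recalls the plan for at least 50 patients and adds that "with as few as 15 patients and an observed favorable outcome rate at 80%, we will have 88% of power". Section 2.3 still states that "The study plans to perform islet transplants for 50 or more patients".

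Section 9.1.1 describes the analysis as estimation: "The primary analysis is to estimate the true rate of this composite favorable outcome at one year". For the interval, "An exact (Clopper-Pearson) two-sided 95% confidence interval will be constructed".

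**The concern.** Section 2.8 does not name the method behind Table 1. Power of 88% at n=15 is higher than a binomial test can give for a null near 50%, a true rate of 80% and a one-sided 5% level. The planned interval is exact, so a large-sample power figure would also not match the analysis.

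The closing sentence is the SAP's only numerical support for the idea that far fewer than 50 patients would suffice. The SAP does not say that enrolment stopped. However, section 2.1 says the series is to be the basis for a biological license application, and a reader relying on this sentence would underestimate the risk of an inconclusive result.

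The row label is a smaller fault of the same kind: power is defined at a true rate, not an observed one.

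**Working it through.** **Inputs**

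- One-sided alpha 0.05; minimal gain 50 points (SAP 2.8). The gain is read as percentage points, the only reading that fits a comparator below 1% and Table 1.
- Comparator rate below 1% (2.8) or 0.3% (2.7.2). The null rate p0 is therefore 0.50 to 0.51. The values checked are 0.50, 0.503, 0.505 and 0.51.
- Expected rate p1 = 0.80; n = 15; stated power 88% (2.8, Table 1).
- Planned interval: exact two-sided 95% (9.1.1).

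**Reproducing the stated figure**

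Wald approximation with the variance taken at the alternative:

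power = Φ((p1 − p0)/√(p1(1 − p1)/n) − 1.645)

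For n = 15 and p1 = 0.80 the standard error is √(0.16/15) = 0.1033. With p0 = 0.505, 0.295/0.1033 = 2.856, then 2.856 − 1.645 = 1.211 and Φ(1.211) = 88.7%. The result is 89.6% at p0 = 0.50 and 87.8% at p0 = 0.51. The largest deviation over all 16 cells is 0.71 point at p0 = 0.505, 1.1 at 0.503, 2.2 at 0.50 and 3.3 at 0.51. A z test with the null variance gives 77.4% to 80.2% for the n = 15, 80% cell, so it does not explain the table.

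**Exact calculation at n = 15**

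| Cutoff | P at null 50% | P at null 51% | Power at true 80% |
|---|---|---|---|
| ≥11 | 1941/32768 = 0.0592 | 0.069 | 83.6% |
| ≥12 | 576/32768 = 0.0176 | 0.0212 | 64.8% |

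A cutoff of 11 breaks the 5% level at every null in the range, so 12 is needed. The power is

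P(X ≥ 12 | 15, 0.80) = 0.2501 + 0.2309 + 0.1319 + 0.0352 = 0.648.

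The cutoff and the power are the same for all four nulls and at one-sided 0.05 or 0.025. The planned interval agrees: the lower 95% Clopper-Pearson limit is 0.519 at 12/15 and 0.449 at 11/15.

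**Does the Wald rule itself deliver 88%?** No. Applied at n = 15, it rejects at 11 successes. Its true power is 83.6% and its type I error is 5.9% to 6.9%.

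**Whole table, stated against exact power (%), one-sided 0.05**

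| n (cutoff) | 65% | 70% | 75% | 80% |
|---|---|---|---|---|
| 15 (≥12) | 32 / 17.3 | 50 / 29.7 | 71 / 46.1 | 88 / 64.8 |
| 20 (≥15) | 39 / 24.5 | 60 / 41.6 | 81 / 61.7 | 95 / 80.4 |
| 30 (≥20, null 50%) | 51 / 50.8 | 75 / 73.0 | 93 / 89.4 | 99.2 / 97.4 |
| 30 (≥21, null 50.3–51%) | 51 / 35.8 | 75 / 58.9 | 93 / 80.3 | 99.2 / 93.9 |
| 50 (≥32) | 70 / 62.2 | 91.5 / 85.9 | 99.1 / 97.1 | >99.9 / 99.7 |

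The rows for 15, 20 and 50 hold for every null from 50% to 51%. The n = 30 row splits because 20/30 gives P = 0.049 at a null of 50% but 0.0528 at 50.3%.

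**Sample size at which 88% is true.** Exact power at a true 80% first reaches 88% at n = 21. It stays at or above 88% from n = 23 (null 50% to 50.3%) or n = 24 (null 50.5% to 51%).

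**The case against.** The strongest reply is that nothing in the analysis depends on the 88%. Section 9.1.1 plans estimation and sets no success threshold, no interim analysis is planned, and the protocol justifies 50 patients by interval width alone. This is correct, and it limits the consequences. It does not make the figure right: the SAP chose to state a power with a threshold and an alpha, and section 9.2 says that hypotheses attach only to the primary analyses.

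A second reply is that the table is consistent with a single formula, so the fault is a choice of method, and Wald is only inferred. That is fair. The best-fitting null of 50.5% appears nowhere in the documents, and the text should say that the table reproduces as a Wald calculation. The exact result does not depend on that inference.

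A third reply is that most of the gap comes from discreteness. About 4 points (88 to 83.6) are approximation error. The other 19 (83.6 to 64.8) come from moving the cutoff from 11 to 12, which leaves a true size of only 1.8% to 2.1%. Power at n = 16 is 79.8%, and a mid-p test at n = 15 would reject at 11/15 (mid-p 0.038 to 0.045) with 83.6% power. All of this is true, and n = 15 is an unlucky sample size. But the planned interval is exact, 15 is the number the SAP chose to cite, and neither alternative reaches 88%.

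Finally, the shortfall is not confined to n = 15 and 20. It reaches 16 points at n = 30 for nulls of 50.3% to 51%, and 7.8 points at n = 50 and a true 65%. That is a reason to recompute the whole table.

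**Conclusion.** The concern holds. With 15 patients and a true rate of 80%, power is 64.8%, about 23 points below the stated 88%. The chance of missing the threshold is about 1 in 3, against the 1 in 8 that 88% implies. Neither the exact test nor the Wald rule gives 88% at n = 15. At n = 20 and a true 80% the shortfall is about 15 points. At the planned n = 50 and the expected 80% it is under 1 point, so the case for 50 patients is unaffected.

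The conclusion rests on two assumptions: success means excluding a rate of 50% to 51%, and the 50% increase is in percentage points. The n = 15 figure does not change across that range of nulls, or between one-sided 0.05 and 0.025. It should be corrected before the SAP is relied on.

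**What to change.** - Recompute all of Table 1 with exact binomial power, and state the null rate, the alpha and the test.
- Say what would count as success. If it is the lower limit of the two-sided 95% Clopper-Pearson interval, use one-sided 0.025. Power at a true 80% is then 64.8% at n = 15; 80.4% at n = 20 (63.0% at a null of 51%); 93.9% at n = 30 (87.1% at a null of 51%); and 99.4% at n = 50.
- Relabel the rows as the true favourable outcome rate.
- Replace the closing sentence with one saying that 15 patients give about 65% power at a true 80% rate to exclude the 50-point threshold by the exact test.
- Optionally, note that ±0.111 at n = 50 is a Wald half-width. The planned exact interval at 40/50 is 0.663 to 0.900, that is about −0.14/+0.10.

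The cost is one recomputed table and a few lines of SAP text. The stated figures become less favourable. No extra patients are needed, and the endpoint, data collection and analysis do not change.

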## **2.9. Changes from the Planned Protocol Analysis**

A second definition of SHE was added in addition to the protocol definition for exploratory analysis. The protocol definition tends to exclude some clinically valid SHEs with a more limiting blood glucose parameter. The purpose of using the second definition is to compare the SHE outcomes by this broader clinical definition with that by the protocol definition, and to demonstrate that the efficacy evaluation is not biased by the differential definitions of SHE.

Evaluation of PRA was omitted in the protocol and is added back as a critical safety endpoint based on its clinical significance.

The original protocol-planned evaluation of primary and secondary endpoints was scheduled at 1 year following the first transplant. The evaluation and analyses are also planned for the time point at 1 year after last transplant in order to take into consideration that patients can have more than one transplant, and thus the 1-year-post-last-transplant evaluation is important in providing adequate efficacy assessment.

For the secondary endpoint based on patient self-monitored post-prandial capillary glucose levels, the evaluation minimum requirement is reduced from three out of 21 times a week to a proportionally one out of every seven times measured. The change is based on the consideration that this piece of information relies totally on patient reported diary data, and frequent and random missing of data is expected. The reduction of minimum data requirement here is an attempt to unbiased efforts in maximizing the reportable results.

